#### 4. LIST of ABBREVIATIONS

AE	Adverse Event
CI	Chief Investigator
GCP	Good Clinical Practice
ICF	Informed Consent Form
IOG	Independent Oversight Group
IAPT	Increasing Access to Psychological Therapies
ISF	Investigator Site File (This forms part of the TMF)
ISRCTN	International Standard Randomised Controlled Trials Number
LEAG	Lived Experience Advisory Group
MiMoS	Mixed Methods of SARCs
NHS R&D	National Health Service Research & Development
PI	Principal Investigator
PIS	Participant Information Sheet
PMG	Programme Management Group
PSC	Programme Steering Group
REC	Research Ethics Committee
SAE	Serious Adverse Event
SARC	Sexual Assault Referral Centre
SOP	Standard Operating Procedure
SSI	Site Specific Information
TMF	Trial Master File
TMG	Trial Management Group
TSC	Trial Steering Committee
WP	Work Package

## 5. STUDY SUMMARY

Study Title	The Effectiveness of S exual Assault Referral Centres with regard to Mental Health and Substance Use: A National M ixed M ethods study
Internal ref. no. (or short title)	MiMoS study
Study Design	Realist Evaluation using Mixed Methods
Study Participants	Sexual Assault Referral Centre's (SARCs) and related service's staff, service users and stakeholders
Planned Study Period	01.06.2018 – 31.05.2021
Research Questions	
 
1. What programmes are identified in published and grey literature to inform how mental health and substance use can be best addressed in SARCs?
 
2. What models can be identified across the SARC services in terms of addressing mental health and substance use?
 
3. What is the prevalence and nature of mental health and substance use in people who attend SARCs?
 
4. What types of services are accessed by people with a range of needs following attendance at a SARC, and how satisfied are they with those services?
 
5. What are the barriers and facilitators to accessing the right support at the right time for people who have attended a SARC?
 
6. How do outcomes differ between a bespoke psychological therapies service at a SARC and mainstream mental health?
 


Research Objectives
	
 
1. To undertake an evidence review of SARC provision for health outcomes (including mental health and substance use) (Work Package 1)
 
2. To identify what models of SARCs currently exist in England (Work Package 2)
 
3. To identify the mental health and substance use needs of attendees of SARCs (Work Package 3)
 
4. To identify what services are available, and to explore satisfaction with care, barriers to access and gaps in provision (Work Packages 2, 3 and 4)
 
5. To understand from the perspective of the workforce and their current practice, skills and training needs in terms of recognition of, and referral for, mental health and substance use issues (Work Package 4)
 
6. To obtain the survivor view on how they felt their emotional well-being was addressed by the SARC as well as external services (Work Package 4)
 
7. To compare health outcomes for people who experience sexual assault and access bespoke SARC psychological therapies provision compared to those who experience sexual assault and are in mainstream mental health services (Work Package 5)
 
8. To produce a range of lay and academic outputs that will aim to identify and share good practice in SARC services related to substance use and mental health in order to have an impact on care delivery (e.g. training materials, new methods of screening, local partnerships etc.) (all Work-Packages, and specifically Work Package 6)
 

----------------------------	--

## 6. FUNDING AND SUPPORT IN KIND

FUNDER(S) (Names and contact details of ALL organizations providing funding and/or support in kind for this trial)	FINANCIAL AND NON FINANCIAL SUPPORT GIVEN
National Institute for Health Research (NIHR)	Total research costs requested (not including NHS Support & Treatment Costs): £1,161,567.21 Total NHS support & treatment costs / (savings): £3,384.00

## 7. ROLE OF TRIAL SPONSOR AND FUNDER

**ROLE OF TRIAL SPONSOR:** The sponsor (The University of Leeds) is responsible for ensuring before a study begins that arrangements are in place for the research team to access resources and support to deliver the research as proposed and allocate responsibilities for the management, monitoring and reporting of the research. The Sponsor also has to be satisfied there is agreement on appropriate arrangements to record, report and review significant developments as the research proceeds, and approve any modifications to the design.

**ROLE OF TRIAL FUNDER:** The funder (National Institute for Health Research (NIHR) HS&DR 16/117/03) is the entity that will provide the funds (financial support) for the conduction of the study. Funders are expected to provide assistance to any enquiry, audit or investigation related to the funded work.

**ROLE OF CHIEF INVESTIGATOR (CI):** The person who takes overall responsibility for the design, conduct and reporting of a study. If the study involves researchers at more than once site, the CI takes on the primary responsibility whether or not he/she is an investigator at any particular site.

The CI role is to complete and to ensure that all relevant regulatory approvals are in place before the study begins. Ensure arrangements are in place for good study conduct, robust monitoring and reporting, including prompt reporting of incidents, this includes putting in place adequate training for study staff to conduct the study as per the protocol and relevant standards.

The Chief Investigator is responsible for submission of annual reports as required. The Chief Investigator will notify the REC of the end of the study, including the reasons for the premature termination. Within one year after the end of study, the Chief Investigator will submit a final report with the results, including any publications/abstracts to the REC.

**ROLE OF WORK PACKAGE LEADS:** Individually or as leader of the researchers at a site; ensuring that the study is conducted as per the approved study protocol, and report/notify the relevant parties – this includes the CI of any breaches or incidents related to the study.

## **8. ROLES AND RESPONSIBILITIES OF TRIAL MANAGEMENT COMMITTEES/GROUPS & INDIVIDUALS**

### **Programme Management Group (PMG)**

The PMG will meet every 2-3 months to ensure all practical details of the trial are progressing and working well and that the project is progressing along its timelines. This group will be formed of the CI, WP Leads and the researchers on the study.

### **Programme Steering Committee (PSC)**

The PSC will meet around every 6 months and includes all members of the PMG as well other stakeholders such including PPI representation, NHS England and Trust PIs. It will provide the overall supervision of the wider programme of research.

### **Independent Oversight Group (IOG)**

The IOG will assess, at intervals, the progress of the research and safety data, to ensure that the continuing trial is safe for those participating. It is completely independent of the investigators, their employing organizations, funders and sponsors. This committee will meet once every 6 months and be available in order to oversee any decisions regarding ethical considerations that occur throughout the trial.

### **Lived Experience Advisory Group (LEAG)**

The Lived experience advisory group will provide expert-by-experience opinion to the research team via face-to-face meetings and through email contact. The committee will comment on research material and protocol and will meet regularly throughout the study.

## **10. KEY WORDS**

Sexual Assault; Mental Health; Substance Misuse; Rape; SARC

# 11. TRIAL FLOW CHART

Flow Diagram

## **12. THE EFFECTIVENESS OF SEXUAL ASSAULT REFERRAL CENTRES WITH REGARD TO MENTAL HEALTH AND SUBSTANCE USE: A NATIONAL MIXED METHODS STUDY**

### **Mixed Methods Study of SARCs (MiMoS)**

#### **12.1. Background**

Sexual assault referral centres (SARCs) are a one-stop shop for the treatment of people who have experienced sexual assault. They bridge criminal justice and health services in recognition of the range of needs that are presented. This includes forensic medical examinations, physical and mental health checks, safeguarding and risk assessment, as well as psychosocial support. SARCs are also able to refer or signpost to other agencies in the local area should a need be identified. The HS&DR has commissioned this research to examine how SARCs are responding to the mental health and substance use needs of its service users.

Mental ill health is common in people who attend SARCs. In Holland (Bicanic et al., 2014), the United States (Brown et al., 2013), and England (Brooker and Durmaz, 2015), approximately 40% of SARCs attendees have been estimated to have a mental health problem. In a recent audit of Thames Valley SARCs, Brooker et al (under review) found: that 69% of attendees could be defined as experiencing a mental health problem; 20% had a history of admission to a psychiatric unit; 32% were drinking at 'hazardous' levels; and 45% had previously self-harmed. In a secondary analysis of data from the Adult Psychiatric Morbidity Survey, Brooker and Tocque (2016) found that there was a consistent relationship between risk of mental health and substance use problems and the level of sexual violence experienced. They concluded that having mental health expertise in SARCs was crucial. However, the National Service Specification for SARCs (NHS England, 2015) whilst acknowledging mental health issues are common, states only that SARCs should ensure the provision of appropriate psychosocial support according to need, and where this exceeds what Increasing Access to Psychological Therapies (IAPT) can support, then they will be referred to secondary mental health services.

In the first national survey of SARCs Brooker and Durmaz (Brooker and Durmaz, 2015) reported that only half of SARCs routinely assessed mental health needs of attendees, and where it was assessed it was completed by a Forensic Medical Examiner (FME). Substance misuse issues were not always included. Almost two-thirds of SARC services report problems in referring on to mental health services for a variety of reasons. The paper argued that more research was needed in this important area and that NHS England should fully describe the skills required to undertake a mental health risk assessment when someone has been the victim of rape or sexual assault.

## **12.2. Rationale**

Despite the high levels of mental health and substance use needs of those who attend SARCs, there is limited evidence regarding the specific needs of people who attend SARCs, what works for whom, in what context, and where resources could be allocated to obtain maximum benefit. In order to do this, we need to identify models of identifying and assessing mental health and/or substance use problems; what subsequent referral pathways are available for a range of people; the views and preferences of people who use SARCs; the workforce needs not only for SARC staff but for the network of agencies that work with survivors (including mental health, third sector counselling and substance use services); and the costs and benefits of different models of service provision.

The aim of the MiMoS study is to generate evidence related to the mental health and substance by addressing the following questions:

1. What programmes are identified in published and grey literature to inform how mental health and substance use can be best addressed in SARCs?
2. What models can be identified across the SARC services in terms of addressing mental health and substance use?
3. What is the prevalence and nature of mental health and substance use in people who attend SARCs?
4. What types of services are accessed by people with a range of needs following attendance at a SARC, and how satisfied are they with those services?

5. What are the barriers and facilitators to accessing the right support at the right time for people who have attended a SARC?
6. How do outcomes differ between a bespoke psychological therapies service at a SARC and mainstream mental health?

### **12.3. Assessment and management of risk**

Conducting research in this population is not without risk to the participants, the researchers and the programme facilitators. The potential risks associated with this trial and more widely in our research group have been considered and guidance has been produced to minimise/mitigate these risks. Safety standard operating procedures will be developed, which all relevant staff (researchers, CRN staff, recruiting SARC staff) will be trained on. All research staff will be familiarised with this protocol and the SOP prior to conducting any trial-related procedure.

### **12.4. Research objectives**

1. To undertake an evidence review of SARC provision for health outcomes (including mental health and substance use) (Work Package 1)
2. To identify what models of SARCs currently exist in England (Work Package 2)
3. To identify the mental health and substance use needs of attendees of SARCs (Work Package 3)
4. To identify what services are available, and to explore satisfaction with care, barriers to access and gaps in provision (Work Packages 2, 3 and 4)
5. To understand from the perspective of the workforce and their current practice, skills and training needs in terms of recognition of, and referral for, mental health and substance use issues (Work Package 4)
6. To obtain the survivor view on how they felt their emotional well-being was addressed by the SARC as well as external services (Work Package 4)

7. To compare health outcomes for people who experience sexual assault and access bespoke SARC psychological therapies provision compared to those who experience sexual assault and are in mainstream mental health services (Work Package 5)
8. To produce a range of lay and academic outputs that will aim to identify and share good practice in SARC services related to substance use and mental health in order to have an impact on care delivery (e.g. training materials, new methods of screening, local partnerships etc.) (all Work-Packages, and specifically Work Package 6).

In order to address these questions and objectives, we will undertake a multi-method study comprising of 6 work packages (WPs). This will include a review of the literature to identify models of good practice in working with mental health and substance use (WP1), then a national survey of all 47 SARCs to identify the ways in which they are recognizing and addressing mental health and substance use (WP2). These two work packages will inform and refine an emerging programme theory that we will further test in work packages 3 and 4. We will select around 6 SARCs to act as case study sites based on a sampling framework established by WP1 and 2. In WP3, we will endeavour to identify the nature of the needs of SARC attendees by undertaking a prevalence study as well as “what works for whom” in a follow-up survey asking about service use and satisfaction following an attendance at SARCs. In WP4 we will undertake more in-depth qualitative work refining and testing patterns that emerge as we undertake and analyze the data. This will comprise of focus groups with providers, individual interviews with service users and their significant others, and documentary analysis. By the end of WP4 we will have a more refined programme theory and will have some conclusions about what works for certain groups of people, what the contexts and mechanisms by which this works as well as recommendations for policy practice and further research. In work package 5 we will interrogate anonymized data sets of routine data for a specific psychological therapies service attached to a SARC as well as a data set of people identified as experiencing a sexual assault but who are within a mental health service. We will work with survivors and practitioner advisors throughout the whole study to ensure that our research is meaningful for those end users, and that we are producing work that has use and relevance to survivors, practitioners and

commissioners. To this end, we have added a specific work package (WP6) to co-produce actionable tools based on the emerging findings working in partnership with survivors and practitioners. As such, the Work Packages will help achieve the research objectives.

A Data Management Plan [MiMoS\_23240\_Data Management Plan\_v1\_16.08.2019] has been developed for WP 3, 4 and 5 to compliment this protocol.

This protocol will outline each work package in detail.

### **13. WORK PACKAGE 1: THE IDENTIFICATION AND TREATMENT OF MENTAL HEALTH AND SUBSTANCE MISUSE PROBLEMS IN SARCS: A SYSTEMATIC REVIEW**

---

WP1 is a systematic review of previously reported studies and will require no ethical approval, or additional consent from participants and is near completion. As such, it is not detailed here. It aims to systematically review the comparative evidence for SARCs regarding mental health and/or substance misuse outcomes and has been registered on Prospero: PROSPERO 2018 CRD42018119706

Available from: [http://www.crd.york.ac.uk/PROSPERO/display\\_record.php?ID=CRD42018119706](http://www.crd.york.ac.uk/PROSPERO/display_record.php?ID=CRD42018119706)

#### **14. WORK PACKAGE 2: THE NATIONAL SURVEY OF SARCS AND MENTAL HEALTH/SUBSTANCE MISUSE**

---

WP2 is a national survey of SARCS examining how they currently respond to mental health and substance misuse which required no ethical approval, or additional consent from participants. As such it is not detailed here. The survey has now been closed. The results have been used to inform case study sampling in WP3 and 4.

## **15. WORK PACKAGE 3: MENTAL HEALTH, SUBSTANCE MISUSE AND SARC ATTENDEES: A PREVALENCE STUDY**

---

### **15.1. Aims**

Work Package 3 has the following aims:

- 1.) To estimate the prevalence of mental health and substance use difficulties in cohort of people attending SARCs
- 2.) To assess how the identified mental health and substance misuse needs have been met at a 6month follow-up point
- 3.) To calculate quality adjusted life years (QALYs) over the 6 months

### **15.2. Study Design**

Cross-sectional prevalence study, with a prospective follow-up cohort study of service use and satisfaction.

### **15.3. Setting**

Participating SARCs at 6 sites across England, with the possibility of adding further sites if needed

### **15.4. Sample**

Adults over the age of 18 who attend SARCs and who consent to participate within the recruitment period (or until sample size is reached).

The Inclusion Criteria are as follows:

- 1.) Aged 18 or older
- 2.) Can read and understand English (or there are suitable confidential translation services available)

The Exclusion Criteria are as follows:

- 1.) Lack of capacity to provide informed consent.
- 2.) Where participation is deemed to significantly increase risk to self or others.
- 3.) Attendee of a SARC not participating in the study

To meet power requirements, a total sample size of n=360 across the six sites should be obtained (n=60 at each site). With an estimated population of 4000 across 6 sites per year, we estimate attendees at each SARC will be 40-60 referrals per site, per month. In a recent 12-month audit of mental health needs in Thames Valley SARCs (Brooker et al., under review) the SARC staff obtained

consent and collected data on 42% of attendees and 38% declined to participate (with limited support to recruit). Therefore we are confident that we should be able to obtain consent from 50% of attendees to participate which means 20-30 per site, per month. If we assume 20 per month (~50%) consent to participate x 6 sites= 120; therefore, sample size would be reached in 3 months; 120 x 3 =360, with 3 months leeway for variation. Extra sites may be added as necessary.

### **15.6. Measures**

The following self-complete outcome measures will be used to assess relevant aspects of mental health and substance misuse.

- Demographics questionnaire
- Mental Health symptoms CORE 10 (Connell and Barkham, 2007) (MAIN OUTCOME)
- Alcohol Screening Tool (AUDIT-C) (Bush et al., 1998)
- The Primary Care PTSD Screen for DSM-5 (PC-PTSD-5) (Prins et al., 2015)
- ReQoL (Quality of Life for mental health) (Keetharuth et al., 2018)
- Drug use (DAST) (Skinner, 1982)
- Standard assessment of personality – a brief screen for personality disorder (SAPAS) (Moran et al., 2003)

These measures (with the exception of demographic questionnaire and SAPAS), will be completed again 6 months following recruitment into the study. At the 6 month follow-up, participants will also complete a bespoke service receipt inventory - designed to collect information on the proportion of different mental health, substance misuse and counselling services used by people in contact with SARC's, along with questions regarding participant's satisfaction and perceptions of unmet need. At this time point, participants will also be asked for meta-feedback about how they felt about the recruitment process and their participation in the study.

## 15.7. Procedure

A period of engagement with each SARC site will be undertaken in order to fully brief the staff about all aspects of the study and training on how to raise awareness of the subject of the study with attendees.

### 15.7.1. Recruitment & Consent

The following recruitment strategy and procedures have been developed in order to empower participants to have control over the decision about their capacity to participate in the research (Perot, Chevous & Survivors' Voices Research Group, 2018). Through engagement with our LEAG group we have developed a variety of recruitment strategies, recognizing that not all potential participants may want to come into the study in the same way. Participants will be able to first engage with the study in several ways:

- 1.) Upon presentation at a SARC participants may give verbal consent to contact to a member of SARC staff. This verbal consent will be recorded in the participant's notes or on the verbal consent to contact form provided to trusts, depending on the preference of the service. This verbal consent to contact will enable the participant to hear about the research from a researcher at a later date, at a time that is acceptable/convenient to them.
- 2.) Participants may give verbal consent to contact via any member of staff at any follow-up time point within the 6 weeks of attending the SARC. Once verbal consent to contact has been given (and documented), the participant can hear about the study from a researcher at a time that is acceptable/convenient to them.
- 3.) Researchers may sometimes be present at SARCs and available to talk with participants at their request. Researchers will be able to provide participants with information about the study (specifically suggested by the LEAG group).
- 4.) Clinical Studies Officers may sometimes be present at SARCs and available to talk with participants at their request. CSOs will be able to provide participants with information and with verbal consent, pass their details onto the researcher who will be able to speak with the participant in more detail about the research

- 5.) Participants may refer themselves to the study. The study will be advertised to eligible participants through social media and posters in relevant areas (for example, within SARCs, third sector organisations) and adverts on relevant websites (survivors trust etc; this was specifically suggested by the LEAG group)
- 6.) Leaflets will be given to all eligible people attending SARCs so that they may self-refer to the study following their visit (this was specifically suggested by the LEAG group).

After the participant has referred themselves to the study or given verbal consent to be contacted by a researcher, researchers will follow the following processes:

- 1.) Participants name and preferred method(s) of contact will be recorded by the research team. The researcher will contact the participant via phone (or post, email or text) to speak with the participant and if they so wish, provide them with all the information necessary for them to make fully informed consent (1-4 weeks after the presentation at SARC). Written information will be provided if safe to do so in the form of a PIS and this will also be verbally discussed. Participants will be given at least 24 hours (or longer if needed/requested) to consider the information before deciding whether or not to take part.
- 2.) If the participant decides to take part in the study, then fully informed consent will be obtained and the baseline study questionnaires will be completed, usually via a link emailed to the participant using University of Leeds approved online survey provider (e.g. 'Online Surveys'). However, if participants prefer, they can also complete the consent forms and questionnaires by post. In this instance, 2 copies of the consent forms signed by the researcher will be sent to participants along with the questionnaire and a stamped addressed envelope. Participants will be instructed to complete the consent forms and questionnaire, returning 1 consent and the questionnaire in the stamped addressed envelope provided. A further option for completing the questionnaires is over the phone with a researcher. In this

instance, the researcher will complete the online consent form and questionnaire over the phone with the participant, obtaining text or email confirmation of consent.

3.) Participants will be followed up 6 months later (using contact preferences obtained at baseline) in order to complete the follow-up questionnaires and service use questions.

Participants will also be asked for meta-feedback about how they felt about the recruitment process and their participation in the study.

When attempting to contact the service user, researchers will use contact preferences up to 5 times before we record as 'unable to contact', in these instances, personal data will be deleted from the database.

The participants will receive £10 for participation in the prevalence study and follow-up, and if required, reimbursement for any additional travel expenses

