### **15.8. Analysis**

The demographics of our prevalence study sample, both non-recent and recent cases, will be initially compared to routine data collected from the 6 sites over the course of the national survey (WP2) in order to assess representativeness of our sample. The final dataset will then be weighted for demographics (e.g. age, gender, deprivation).

A direct estimate of the prevalence of mental health within SARC attendees will be determined from the sample and weighted estimates produced for the 6 SARC sites. Additionally, a further weighted national estimate will be produced (if demographic data can be obtained for all 47 SARC sites).

Analysis of other health, wellbeing and behavioral measures will follow the same principle to produce direct (and site-specific and national weighted) estimates. Prior to producing these estimates, the dataset will be analyzed to determine how/if demographics, site or method of data collection have influenced prevalence measures. A logistic multivariate analysis will be undertaken to determine predictors of mental health and/substance use diagnosis. Participant's feedback on satisfaction with services and any gaps/unmet need will also be analyzed descriptively and themed in order to glean qualitative insights.

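### WP3 can recruit at SARC follow-up contacts as well as at presentation, so entry may depend on early contact with the service, and the plan's demographic weights would not correct the 6-month service results for that

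*Protocol*

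**What the plan says.** Protocol 15.7.1 lists six ways into WP3. The first is at attendance: "Upon presentation at a SARC participants may give verbal consent to contact to a member of SARC staff". The second adds "verbal consent to contact via any member of staff at any follow-up time point within the 6 weeks" after that attendance. Researchers and Clinical Studies Officers may also be present at the centre. Two routes need no later contact with the SARC: "Leaflets will be given to all eligible people attending SARCs so that they may self-refer to the study following their visit", and self-referral, for which "The study will be advertised to eligible participants through social media and posters in relevant areas" and on relevant websites.

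At 6 months a service receipt inventory (15.6) collects "the proportion of different mental health, substance misuse and counselling services used by people in contact with SARC's". The same follow-up also covers how participants judge that care: "along with questions regarding participant's satisfaction and perceptions of unmet need". These data serve the second WP3 aim (15.1), which is how far identified needs have been met. Section 15.9 adds costs, and asks whether engagement with services predicts quality of life.

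On representativeness, 15.8 compares the sample's demographics with routine site data and then states: "The final dataset will then be weighted for demographics (e.g. age, gender, deprivation"). It also examines whether demographics, site or method of data collection influenced the prevalence measures. Recruitment route and contact with the SARC after presentation are not named. The multiple imputation in 15.9 is for recruits with missing 6-month data, not for attendees who never entered.

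**The concern.** An attendee with no contact after presentation can be approached by staff only once. One who stays in contact can be approached then or later. If both kinds of occasion are used, the chance of entering WP3 rises with early SARC contact. Early SARC contact may also be related to use of mental health, substance misuse and counselling services over the next 6 months, which is what the inventory measures. Selection would then be related to the outcome.

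Demographic weights remove only the part of that relation that runs through age, gender, deprivation and similar variables. At stake are the descriptive service use and cost results, and possibly satisfaction and unmet need. They bear on the research question about services accessed and satisfaction, and attendees who drop out of contact are the people a study of access most needs to represent. If contact status is not captured at entry, a later analysis plan has nothing to adjust on.

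**Working it through.** **Plan's own figures.** 20 per site per month × 6 sites × 3 months = 360, and 60 × 6 = 360. 4000 / 6 / 12 = 55.6 attendees per site per month, inside the stated 40–60, and 50% of 40–60 is 20–30. The recruitment arithmetic reproduces. The inputs taken from it are n = 360 and 50% participation (15.4).

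**Assumed inputs (none is in the protocol).** Share of attendees with follow-up contact, e: 30%, 50% or 70%. Extra approaches they receive, k: 0.5, 1 or 2. Later service use with and without follow-up contact: 70% v 30% (strong link) or 60% v 50% (weak link).

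**Model.** Entry probability is p with one approach and 1 − (1 − p)^(1+k) with k extra. Solve e[1 − (1 − p)^(1+k)] + (1 − e)p = 0.50 for p. The sample share with follow-up contact is then s = e[1 − (1 − p)^(1+k)] / 0.50. The bias in service use is (s − e) × (difference in use between the groups).

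Worked case, e = 0.5 and k = 1: p = 0.382, entry with contact = 1 − 0.618² = 0.618, s = 0.618. Strong link: 0.118 × 0.40 = 4.7 points. Weak link: 0.118 × 0.10 = 1.2 points.

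| e | k | entry ratio | s | bias, 70% v 30% | bias, 60% v 50% |
|---|---|---|---|---|---|
| 0.3 | 0.5 | 1.31 | 0.360 | +2.4 | +0.6 |
| 0.3 | 1 | 1.57 | 0.403 | +4.1 | +1.0 |
| 0.3 | 2 | 1.99 | 0.461 | +6.4 | +1.6 |
| 0.5 | 0.5 | 1.32 | 0.570 | +2.8 | +0.7 |
| 0.5 | 1 | 1.62 | 0.618 | +4.7 | +1.2 |
| 0.5 | 2 | 2.15 | 0.682 | +7.3 | +1.8 |
| 0.7 | 0.5 | 1.34 | 0.757 | +2.3 | +0.6 |
| 0.7 | 1 | 1.66 | 0.795 | +3.8 | +0.9 |
| 0.7 | 2 | 2.28 | 0.842 | +5.7 | +1.4 |

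Bias is in percentage points.

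**Sampling error for comparison.** 1.96 × √(0.5 × 0.5 / 360) = 5.2 points. It is wider at 6 months after losses. A larger sample would narrow it but leave the bias unchanged.

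**Do demographic weights help?** Assume two equal demographic strata with 60% and 40% having follow-up contact, p = 0.4, one extra approach (entry 1 − 0.6² = 0.64), and use 70% v 30%. True use is 50.0%.
- Inclusion: 0.6 × 0.64 + 0.4 × 0.4 = 0.544 and 0.4 × 0.64 + 0.6 × 0.4 = 0.496.
- Share with contact in the sample: 0.384 / 0.544 = 0.706 and 0.256 / 0.496 = 0.516.
- Service use: 0.3 + 0.4 × 0.706 = 58.2% and 0.3 + 0.4 × 0.516 = 50.6%.
- Unweighted: (0.544 × 58.2 + 0.496 × 50.6) / 1.04 = 54.6%.
- Weighted back to equal strata: 54.4%.
- Weighted by inverse inclusion probability: 50.0%.

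**Do the open routes cancel it?** Take e = 0.5, p = 0.4 and one extra approach: s = 0.64 / (0.64 + 0.40) = 0.615. If leaflets and self-referral give both groups the same extra chance of 0.2, entry is 1 − 0.36 × 0.8 = 0.712 and 1 − 0.6 × 0.8 = 0.52, so s = 0.712 / 1.232 = 0.578. The tilt shrinks but remains. If only those without follow-up contact gain an extra chance of 0.1, 0.2, 0.3 or 0.4, s falls to 0.582, 0.552, 0.525 or 0.500. It vanishes only at about 0.4.

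**The case against.** The protocol does not say staff ask at every contact. The second route can be read as a deferred approach for people not asked at presentation, and a follow-up point might be a call made to every attendee. If all were reached equally, the tilt would shrink or disappear. This stands, and it is why the point is conditional.

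A reader might infer that service access, satisfaction and costs will all be overstated. The documents do not support that. The inventory covers mental health, substance misuse and counselling services and does not name SARC follow-up, so the link between them is an assumption. People who do not return may already be under other services: the audit cited in 12.1 found 20% with a past psychiatric admission. The direction for satisfaction, unmet need and cost is therefore unsettled.

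A reader might also reach larger figures by assuming 20% consent per approach and three approaches. That implies overall participation of only 0.3 × 0.488 + 0.7 × 0.20 = 29% to 0.5 × 0.488 + 0.5 × 0.20 = 34%, against the planned 50%. The model also treats someone who has refused as equally likely to agree next time, which inflates the gain from repeat approaches.

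Satisfaction and unmet need are to be described and themed, and WP4 can recruit outside WP3, so WP3 is not the only evidence on access. Finally, extra weighting variables are commonly left to an analysis plan. That holds for the choice of margin, but not for data that must be captured at entry, and the examples in 15.8 are confined to demographics.

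**Conclusion.** The point holds as a conditional risk. The recruitment routes allow entry to depend on early SARC contact, and the stated weighting would not correct for it. Whether the service use results are in fact tilted depends on three things the protocol does not give: how often staff approach people again, how many attendees have follow-up contact, and how strongly that contact goes with later service use. At 50% participation, and with the open routes left out, the overstatement is 0.6 to 1.8 points with a weak link and 2.3 to 7.3 with a strong one. It reaches about 6 to 7 only with two extra approaches and a strong link. Against a half-width of about 5 points, it ranges from negligible to somewhat larger than sampling error. This analysis does not challenge the CORE-10 main outcome. The point is a cheap improvement, not a design failure.

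**What to change.** Keep all recruitment routes. Add two fields at entry: the route by which the person came in, and whether they had any SARC follow-up contact within 6 weeks of attending. For someone who enters before 6 weeks, complete the second field when that window closes. In 15.8 and 15.9, state that the 6-month service use, cost, satisfaction and unmet need results will be reported by follow-up contact status. Where a site can supply the proportion of its adult attendees with a follow-up contact, add it as a weighting margin in a sensitivity analysis of service use and cost. This step must be conditional, because nothing in the protocol shows that sites hold the count.

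The cost is two extra fields, a request to each site, a few sentences of protocol text and somewhat more variable weights in the sensitivity analysis. The fields need to be in place before recruitment, since contact status may be hard to recover afterwards.
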